### 8.8.6 Physical Examination

Physical examinations will be performed at the following time-points:

- Screening Visit
- Day 42 ± 7 days (for patients with nephrectomy within 28 days p.a.)
- 35 ± 7 days after surgery (for patients with nephrectomy from 28 to 90 days p.a.)

The physical examination will consist of general appearance, orientation to time, space and person, cardio-pulmonary auscultation, manual abdominal examination, and further investigation of any abnormal system, as appropriate.

### 8.8.7 HACA Determination in Serum

In order to detect possible formation of antibodies against girentuximab, serum samples will be collected at Screening, on Day 42 ± 7 days p.a. and at the final study visit.

The final study visit will be conducted in relation to the scheduled nephrectomy.

- i) If the scheduled nephrectomy occurs > 28 day p.a. (i.e., between 28 and 90 days p.a.), the final study visit and the blood draw for HACA serum sample will be on Day 35 ± 7 days *after surgery*.
- ii) If the scheduled nephrectomy occurs ≤ 28 days p.a. (i.e. within 28 days p.a.), the final study visit and the blood draw for HACA serum sample will be on Day 42 ± 7 days *after administration*.

Blood sampling will be  $\leq 3$  mL per sample.

An approximately 2 mL blood sample will be collected in an unheparinized (clotted) tube, stored overnight at 2-8°C and centrifuged at 1000-2000 rpm for 10 minutes. Three 200  $\mu$ L serum aliquots will be transferred into three separately labelled 2 mL cryo-vial and stored at -20°C. Please refer to the central laboratory manual for details on shipping.

The presence of HACA in sera of patients will be tested quantitatively and qualitatively using validated ELISAs in the Bioanalytics Department of Agilex Biolabs Pty Ltd, South Australia, Australia.

## 8.9 Total Volume of Blood

A summary of the blood to be collected from each patient in this study is presented in Table 4. The maximum total volume of blood to be collected from patients over the study period will be 115 mL. For patients who will have their final study visit at Day 42  $\pm$  7 days, 18 mL of blood less will be drawn amounting to a total of 97 mL.

**Table 4 Summary of Blood Volumes Collected for Each Patient**

Sample	Volume per sample	Number of samples	Total volume
Clinical laboratory tests:			
Screening (incl. $\beta$ -HCG)	23 mL	1	23 mL
Day 0, pre-dose	20 mL	1	20 mL
Day 5 $\pm$ 2 days	18 mL	1	18 mL
Day 42 $\pm$ 7 days	18 mL	1	18 mL
Up to 10 days before surgery, including the day of surgery	18 mL	1	18 mL
Final visit (on Day 35 $\pm$ 7 days after surgery, if not Day 42 $\pm$ 7 days)	18 mL	1	18 mL
Overall TOTAL	-	-	115 mL

## 8.10 Total Radiation Exposure

The Zr-TLX250 related radiation exposure will be 37 MBq (+/-10%) per single administration.

The combined whole body effective dose of Zr-girentuximab administration and abdominal low-dose CT is expected to be below 20 mSv based on the accepted standard OLINDA 1.1 and ICRP 60, or below 23 mSv based on IDAC-Dose 2.1 and ICRP 103, for all patients (Section 1.3).

Patients with suspected metastatic disease may undergo an additional whole body PET/low dose CT at the discretion of the Principal Investigator. The additional radiation of this optional imaging is approx. 3 mSv.

## 9 Statistical Methods and Determination of Sample Size

The study design, statistical hypotheses, sample size calculations, and statistical methods selected for this study are based on previous scientific advice granted by the US Food and Drug Administration (FDA) for a planned confirmatory study with girentuximab as an imaging agent.

### 9.1 List of Variables and Population Characteristics

#### 9.1.1 Co-Primary Variables

The primary study objective is to evaluate the diagnostic efficacy in all patients by comparing the sensitivity and specificity of Zr-TLX250 PET/CT imaging to thresholds of 0.70 (sensitivity) and 0.68 (specificity), using histology as standard of truth.

The co-primary variables of this study will be the sensitivity and specificity of Zr-TLX250 PET/CT imaging to detect ccRCC.

- a) Sensitivity is defined as the proportion of study patients with a true positive (TP) Zr-TLX250 PET/CT scan (detection of clear cell carcinoma), relative to those with positive histopathological diagnosis for ccRCC:

$$\text{Sensitivity (\%)} = \text{TP} / (\text{TP} + \text{FN})$$

- b) Specificity is defined as the proportion of study patients with a true negative (TN) Zr-TLX250 PET/CT imaging result (no ccRCC), relative to those with a negative histopathological diagnosis of non-ccRCC (histological result:= TN + FP):

$$\text{Specificity (\%)} = \text{TN} / (\text{TN} + \text{FP})$$

The sensitivity and specificity of Zr-TLX250 PET/CT imaging will be compared separately to their respective prespecified thresholds. The comparison of sensitivity/specificity data will be based on data from the following 2x2 table (Table 5) which summarises the results of the qualitative Zr-TLX250 tumour targeting (tracer uptake in target lesion: yes/no) as determined by visual reading and the central study pathology as standard of truth.

**Table 5 Probability Calculated on All Cases with Positive Histopathology**

		Reference Standard Histopathology (standard of Truth)		Total
		positive (ccRCC)	negative (no ccRCC)	
Outcome  Zr-TLX250 PET/CT scan	positive (ccRCC)	TP	FP	# of cases with positive PET/CT: TP+FP
	negative (no ccRCC)	FN	TN	# of cases with negative PET/CT: FN+TN
total		# of cases with ccRCC TP+FN	# of cases without ccRCC FP+TN	N

Abbreviations: FN = false negative; FP = false positive; TN = true negative; TP = true positive;

The point estimate of sensitivity of PET/CT is TP/(TP+FN) and the point estimate of specificity is TN/(TN+FP). Wilson's binomial (score) confidence intervals will be used to compare the 95% confidence interval lower boundary of each quantity to the threshold of 0.70 (sensitivity) and 0.68 (specificity).

Note that both sensitivity and specificity will be determined for each of three independent readers. The study will be successful if the lower bounds of the 95% confidence intervals (CIs) for sensitivity (>70%) and specificity (>68%) in at least the same 2 out of 3 independent readers.

### 9.1.2 Secondary Variables and Exploratory Analyses

To investigate diagnostic performance in the subgroup of patients with small lesions (cT1a, dimension ≤ 4 cm in longest diameter), sensitivity and specificity with corresponding Wilson (score) 95% CIs will be calculated for such patients.

In addition to the primary efficacy parameters (sensitivity, specificity), the positive predictive value, the negative predictive value and the accuracy will also be calculated as secondary efficacy parameters using data from patients in the subgroup of tumours ≤ 4 cm in largest diameter. Sensitivity and specificity in the cT1a group will be the key secondary endpoints; while positive predictive value, the negative predictive value and the accuracy in the cT1a group will be additional secondary endpoints.

#### 9.1.2.1 Predictive Values and Accuracy

##### a) Positive predictive value (PPV)

The positive predictive value is defined as the probability that a positive histopathology diagnosis was obtained given that the result of the Zr-TLX PET/CT scan is positive (detection of ccRCC).

$$\text{PPV (\%)} = \text{TP} / (\text{TP} + \text{FP})$$

##### b) Negative predictive value (PPV)

The negative predictive value is defined as the probability that a negative histopathology diagnosis was obtained given that the result of the Zr-TLX250 PET/CT scan is negative (no detection of ccRCC).

$$\text{NPV (\%)} = \text{TN} / (\text{TN} + \text{FN})$$

c) Accuracy

The accuracy or probability of a correct test result is defined as the probability that the Zr-TLX250 PET/CT scan result is correct, i.e. the probability that the PET/CT scan is positive if the histopathological diagnosis for ccRCC is positive or that the PET/CT scan is negative if the histopathological diagnosis for ccRCC is negative.

$$\text{Accuracy (\%)} = \text{TP} + \text{TN} / (\text{TP} + \text{FP} + \text{TN} + \text{FN})$$

### 9.1.2.2 Standardized Uptake Value (SUV)

Zr-TLX250 SUVs will be determined for each tumour lesion. Receiver operating characteristics (ROC) will be analysed, to identify a SUV cut-off value, most appropriate to discriminate between ccRCC or non-ccRCC as evidenced by central histology results.

$$\text{SUV} = C_{\text{image}} / (\text{injected dose} / \text{body weight})$$

### 9.1.2.3 Inter-reader Variability

Fleiss' kappa statistics will be used to determine the agreement between the qualitative visual assessment of Zr-TLX250 tumour targeting (tracer uptake in target lesion: yes/no), as assessed by three independent blinded readers (section 8.2.2.4). An intra-class kappa of 0.70 or higher will be considered as an acceptable value. Note that both sensitivity and specificity will be determined for each of three independent readers. The study will be successful if the lower bounds of the 95% confidence intervals (CIs) for sensitivity (>70%) and specificity (>68%) in at least the same 2 out of 3 independent readers.

### 9.1.2.4 Intra-reader Variability

Intra-reader variability will be assessed by having each of the 3 independent blinded readers perform 2 image evaluations on a randomly selected set of 10% cases. A washout period will be introduced between the two interpretations to minimize recall bias. The percent of agreement between the two interpretations will be computed for each reader. Cohen's kappa statistics will be used to determine the reproducibility of the qualitative visual assessment by individual readers when analysing the same data repeatedly.

### 9.1.2.5 Sub group Analysis

Evaluation of sensitivity and specificity of Zr-TLX250 PET/CT imaging to detect ccRCC in patients with IRMs ≤ 3 cm, IRMs ≤ 2 cm, and Bosniak 3 and 4 lesions, as follows:

- 1) Bosniak 3 and 4 lesions (as determined by the independent central readers)
- 2) Indeterminate renal masses ≤ 3 cm in largest diameter (as determined by the independent central readers)
- 3) Indeterminate renal masses ≤ 2 cm in largest diameter (as determined by the independent central readers)

### 9.1.2.6 Safety

a) General safety parameters:

Frequency of occurrence and severity of abnormal findings in safety investigations (physical examination, vital signs, 12-lead ECG, clinical laboratory, urinalysis, adverse events, concomitant medication)

b) HACA testing

### 9.1.2.7 Exploratory Variables

In situ biological half life of girentuximab protein in tumour lesions will be estimated, using a general model of average girentuximab kinetics in tumour tissue, derived from serial Zr-TLX250 imaging. Based on (a) protein residence times in the lesions, (b) an assumed specific activity of therapeutic labelling with Lutetium-177 (Lu), and (c) the measured tumour lesion volume (CT dimensions), an achievable therapeutic absorbed dose to tumour (Gy), will be determined for several specific activities and hypothetical activity doses of Lu.

Exploratory analyses will be delineated in more detail in the Statistical Analysis Plan (SAP) prior to analysis including extra-renal lesions used as a histology standard of truth (when N1 or M1 disseminated disease is suspected)

Additional exploratory investigations correlating the Zr-TLX250 tumour lesion SUVs, semi-quantitation of CAIX expression as determined by immunohistochemistry, and evaluation of the distant masses outside the kidney identified on Zr-TLX250 whole body PET/CT in patients with unexpected evidence of disseminated disease will be conducted.

### 9.1.3 Population Characteristics

Population characteristics will include:

- Clinical suspicion of ccRCC due to imaging evidence of indeterminate renal mass of  $\leq 7$  cm (stage cT1)
- Scheduled for total or partial nephrectomy as part of regular diagnostic work-up at a given date

Summary tables and listings will be provided for demographics and other baseline characteristics, including:

- Age, ethnic origin, sex, physical exam
- Medical/surgical history and baseline findings
- Prior and concomitant medication

## 9.2 Statistical and Analytical Plans

A detailed description of the study analyses and statistical methods will be presented in the Statistical Analysis Plan (SAP). The SAP will be finalized by the study physician and approved by the sponsor prior to the start of the statistical analysis.

### 9.2.1 General Considerations

The aim of this study is to evaluate sensitivity, specificity, PPV, NPV, as well as accuracy of Zr-TLX250 PET/CT imaging using a 37 MBq (1 mCi) activity dose to detect ccRCC in patients with IRM of stage cT1, and who are scheduled for partial or total nephrectomy.

Histological confirmation from nephrectomy (or biopsies of extrarenal lesions from patients in whom unexpected evidence of disseminated disease is observed) will serve as standard of truth. The qualitative Zr-TLX250 PET/CT imaging assessments of 3 independent readers will be the primary imaging result.

All data will be listed and trial summary tables will be provided. Descriptive statistics will be presented. Secondary variables will be summarized. The statistical evaluation will be performed by using SAS® statistical software (version 9.4, or higher).

### 9.2.2 Analysis Sets

The Full Analysis Set (FAS) will consist of all enrolled patients who have evaluable PET/CT imaging and have a confirmed histopathology diagnosis (Table 2).

The Safety Analysis Set (SAF) will consist of all patients who received Zr-TLX250.

The Screening Analysis Set (for CONSORT-style accounting of subject disposition) will consist of all patients assigned a Patient Number (section 4.4).

All primary and secondary efficacy analyses will be carried out using the FAS.

### 9.2.3 Statistical Analyses

Statistical analyses will be performed after database lock, after all study data including the final study visit have been collected and cleaned.

For all variables (primary and secondary), the statistical analyses in this study will be descriptively using exploratory statistics.

Descriptive analyses will include:

- Mean, standard derivation, median and range for continuous variables,
- Median, range and frequency distribution for discrete (ordinal) variables,
- Frequency distribution for nominal variables

#### 9.2.3.1 Analysis of Primary and Key Secondary Objectives

Within this trial, two co-primary endpoints (sensitivity and specificity) shall be analysed.

The analysis for sensitivity uses only those patients with a positive histopathological diagnosis of clear cell carcinoma. These are expected to be about 70% of the included patient population. Sensitivity of Zr-TLX250 will be considered adequate if the **lower boundary of a 95% Wilson (score) confidence interval for sensitivity is higher than 0.7** for at least the same two of three independent readers.

The analysis for specificity uses only those patients with a negative histopathological diagnosis of clear cell carcinoma. These are expected to be about 30% of the included patient population. Specificity of Zr-TLX250 will be considered adequate if the **lower boundary of a 95% Wilson (score) confidence interval for specificity is higher than 0.68** for at least the same two of three independent readers. Two-sided tests will be consistently used in the evaluation.

To account for multiplicity and to control Type I error under the paradigm of two co-primary endpoints, sensitivity and specificity will each be estimated at the 5% significance level. For the study to be deemed successful, the lower limit of the 95% Wilson confidence interval for both sensitivity and specificity must exceed their respective pre-specified thresholds.

Assuming the null hypothesis is rejected for both co-primary endpoints, formal statistical testing will proceed to the family of Key Secondary Endpoints (i.e., sensitivity and specificity in the cT1a group). Within this family, the fixed-sequence method will first assess sensitivity, followed by specificity. Results pertaining to specificity will only be considered formal evidence if the null hypothesis pertaining to sensitivity is rejected.

Additional details will be provided in the SAP.

### 9.3 Determination of Sample Size

It is planned to include approximately 252 evaluable patients in the study.

#### 9.3.1 Sample Size Estimation

The study sample size for the population of patients with indeterminate renal mass (i.e., patients with cT1 tumors) has 2 components: Sensitivity and Specificity. Sample size is estimated for Sensitivity and Specificity, respectively, and the larger of the two estimates will represent the final study sample size. The basic assumptions underlying sample size estimation are the following:

- In the population of patients with indeterminate renal mass (i.e. cT1 patient population), approximately 70% are cT1a and 30% are cT1b patients.
- In the cT1a subpopulation, approximately a third (34%) are expected to show no signs of renal cell carcinoma following histopathology assessment (i.e. ccRCC negative).
- It is expected from a clinical standpoint that the subpopulation of cT1b patients would show a much lower rate of negative histopathologies than the cT1a subpopulation. For the purpose of powering this trial, it is assumed that the rate of non-ccRCC histopathologies in the cT1b subpopulation would be at least 17%, half the rate in the cT1a subpopulation.

**Sensitivity:** to ensure the study has 90% power to show that the lower limit of the 2-sided 95% confidence interval (Wilson) for sensitivity is above the critical limit (or non-inferiority limit) of 70%, the minimum sample size required for the population of cT1 patients under above assumptions is 125, when assuming a true sensitivity of 83%.

**Specificity:** to ensure the study has 90% power to show that the lower limit of the 2-sided 95% confidence interval (Wilson) for the specificity is above the critical limit (or non-inferiority limit) of 68%, the minimum sample size required for the population of cT1 patients under above assumptions is 252, when assuming a true specificity of 83%.

An estimated total of 252 patients with an IRM of  $\leq 7$  cm and scheduled partial or radical nephrectomy will be included in the study. However, in order to maintain adequate study power, this number may be increased depending on the proportion of non-ccRCC patients after surgery and histological verification.

Table 6 provides an example of the expected sample size required with different observed non-ccRCC rates.

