
Study design
	
This will be a confirmatory, prospective, open-label, multi-centre phase 3 study to evaluate sensitivity and specificity of Zr-TLX250 PET/CT imaging to non-invasively detect clear cell renal cell cancer (ccRCC) in adult patients with indeterminate renal masses (IRM), scheduled for partial or total nephrectomy.
 
Histological confirmation will serve as standard of truth, to assess sensitivity, specificity, positive predictive value (PPV), negative predictive value (NPV), as well as accuracy of Zr-TLX250 PET/CT imaging.
 
According to current clinical practice in most specialist centres, patients with an IRM of <math>\leq</math> 7 cm in largest diameter (stage cT1, encompassing the subgroups cT1a <math>\leq</math> 4 cm, and cT1b <math>></math> 4 cm to <math>\leq</math> 7cm), restricted to the kidneys are routinely subjected to partial or total nephrectomy, as this intervention has curative potential in most cases.
 
For that reason this study will be conducted in patients with IRM of stage cT1, and histological material will be obtained as part of routine nephrectomy, circumventing the need for study-specific invasive procedures. Given a reported high rate of non-diagnostic kidney biopsies, patients scheduled to undergo kidney biopsy only, rather than nephrectomy are not eligible for this study.
 
The proportion of patients with a stage cT1 IRM, who actually do not have ccRCC (non-ccRCC patients, i.e. those in whom following surgical removal, ccRCC can be histologically ruled out) has been reported to range between 20–40%. This proportion appears to be higher in smaller (cT1a), compared with larger (cT1b) lesions.
 
For a total study population of cT1 patients composed of 70% of the cT1a subgroup (IRM <math>\leq</math> 4 cm), and assuming 34% non-ccRCC in the cT1a subgroup, a total sample size of 252 patients provides 90% power to confirm both a sensitivity and specificity of 83%, as previously reported for cT1a lesions for prior GTX-based imaging agents (I-girentuximab, In-girentuximab). The total sample size of 252 gives 90% power to distinguish a 68% specificity threshold, assuming a non-ccRCC rate in the cT1b subset of at least 17%.
 
In order to ensure that a sufficient number of patients with cT1a tumour stage and sufficient patients with non-ccRCC histopathology will be included into the total study population, patient accrual and histological results will be centrally evaluated and monitored by an Independent Data Monitoring Committee (IDMC); recruitment into the study will continue until the minimum required number of patients has been recruited. The IDMC members will not have access to Zr-TLX250 PET/CT images, nor will they have access to the PET/CT results from the independent image reviewers.

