**Clinical Study Protocol**  
**Zr-TLX250-003**

Version: 8.0  
Date: 01-Apr-2022

Number of patients	
Total: approximately 252 patients scheduled for partial or total nephrectomy
 
Sample Size: The total number of patients expected to be enrolled is n=252: it is expected that these will include 194 patients with cT1a tumours and 58 patients with cT1b tumours With 194 patients with cT1a tumours it is expected that these will include at least the required number of 128 patients that are ccRCC positive and 66 patients that are ccRCC negative. Based on the actual number of patients observed during trial enrolment with cT1a tumours that are ccRCC positive and ccRCC negative, the total sample size might need to be increased to ensure the minimum of at least 128 and 66, respectively. Therefore, the distribution of enrolled patients will be centrally monitored (reviewing of staging and histology (without imaging results)).
									
Co-primary variables	
Sensitivity and Specificity of Zr-TLX250 PET/CT imaging to detect ccRCC
 
These will be determined, considering the histological diagnosis (ccRCC+ or ccRCC-) as determined by the central study pathology as standard of truth, and the qualitative Zr-TLX250 tumour targeting (tracer uptake in target lesion: yes/no), as determined by visual reading, to yield a 2 x 2 table as follows:
 
  
 	ccRCC+	ccRCC-	
   
 PET+	TP	FP	
 
 PET-	FN	TN	
  
 
Abbreviations: FN=false negative; FP=false positive; TN=true negative; TP=true positive
 
a) Sensitivity will be the proportion of study patients with a true positive (TP) PET scan, out of those with positive histology for ccRCC Sensitivity (%) = TP / (TP + FN)
 
b) Specificity will be the proportion of study subjects with a true negative (TN) PET scan, out of those with negative histology for ccRCC Specificity (%) = TN / (TN + FP)
		ccRCC+	ccRCC-	PET+	TP	FP	PET-	FN	TN
	ccRCC+	ccRCC-								
PET+	TP	FP								
PET-	FN	TN								

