**Table 6: Planned sample size estimates\***

	Outcome	Null	Alt.	Non-ccRCC Rate in CT1a Group	Non-ccRCC Rate in CT1b Group	Alpha	Power	N Total
Scenario (1)	Specificity	0.68	0.83	0.34	0.17	0.05	0.90	252
	Sensitivity	0.70	0.83	0.34	0.17	0.05	0.90	125
Scenario (2)	Specificity	0.68	0.83	0.25	0.20	0.05	0.90	284
	Sensitivity	0.70	0.83	0.25	0.20	0.05	0.90	116
Scenario (3)	Specificity	0.68	0.83	0.25	0.15	0.05	0.90	317
	Sensitivity	0.70	0.83	0.25	0.15	0.05	0.90	114

\* Sample size estimates to achieve 90% power based on rates of non-ccRCC in both CT1a and CT1b groups. Scenario (1) represents the originally planned sample size; while Scenario (2) and Scenario (3) provide potential sample size updates based on different non-ccRCC rates.

Note that both sensitivity and specificity will be determined for each of three independent readers. The study will be successful if the lower bounds of the 95% confidence intervals (CIs) for sensitivity (>70%) and specificity (>68%) in at least the same 2 out of 3 independent readers.

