5 STUDY DESIGN AND SCHEDULE OF ASSESSMENTS

5.1 Study Design

This will be a confirmatory, prospective, open-label, multi-centre phase 3 study (ZIRCON) in adult patients with pre-study imaging evidence of indeterminate renal masses (IRM) of ≤ 7 cm in largest diameter, and scheduled for partial or total nephrectomy as part of their standard of care. The study is designed to evaluate sensitivity and specificity of ⁸⁹Zr-TLX250 PET/CT imaging to non-invasively detect clear cell renal cell cancer (ccRCC).

Histological confirmation will serve as standard of truth, to assess sensitivity, specificity, positive predictive value (PPV), negative predictive value (NPV), as well as accuracy of ⁸⁹Zr-TLX250 PET/CT imaging. Consequently, this study will be conducted in patients with IRM of stage cT1, in which histological material is obtained as part of routine nephrectomy, circumventing the need for study-specific invasive procedures. Given a reported high rate of non-diagnostic kidney biopsies, patients scheduled to undergo kidney biopsy only, rather than nephrectomy are not eligible for this study.

Approximately 252 adult patients were originally planned to be recruited in 35 – 40 renal cancer care specialist centres in Europe (Belgium, France, Spain, the Netherlands), UK, Turkey, Australia, Canada and USA, who have access to state-of-the-art PET/CT imaging. The number of enrolled patients was increased to 300 by a protocol version 8 amendment 7 to ensure adequate precision in measuring both sensitivity and specificity of ⁸⁹Zr-TLX250PET/CT imaging.

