6 PATIENT SELECTION

It is planned to have 300 adult patients with an indeterminate renal mass (IRM) on standard of care imaging, obtained at pre-study, and who are clinically suspicious for renal cell carcinoma and scheduled for partial or total nephrectomy as part of their regular diagnostic work-up/clinical care.

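### The 90% specificity power stated at N = 252, 284 and 317 is about 83%, 80% and 81% per reader under the plan's own two-sided 95% Wilson rule

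*Protocol*

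**What the plan says.** Protocol section 9.3.1 sizes the trial separately for sensitivity and specificity and takes the larger N. For specificity the target is 90% power that the "lower limit of the 2-sided 95% confidence interval (Wilson) for the specificity is above the critical limit (or non-inferiority limit) of 68" per cent, and the "minimum sample size required for the population of cT1 patients under above assumptions is 252, when assuming a true specificity of 83" per cent. Section 9.2.3.1 uses the same criterion for the analysis: the "lower boundary of a 95% Wilson (score) confidence interval for specificity is higher than 0.68", for at least the same two of three readers, with two-sided testing throughout.

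Table 6 gives specificity Ns of 252, 284 and 317 for three sets of non-ccRCC rates, with a footnote calling them "Sample size estimates to achieve 90% power based on rates of non-ccRCC in both CT1a and CT1b groups". All three rows use null 0.68, alternative 0.83, alpha 0.05 and power 0.90. SAP section 7 and SAP Table 2 repeat the text and the table. The synopsis (Study design) also says that "a total sample size of 252 patients provides 90% power to confirm both a sensitivity and specificity of 83" per cent.

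Two other statements matter:
- **Case mix.** Section 9.3.1 assumes 70% cT1a and 30% cT1b. For the same 252 patients, the synopsis (Number of patients) says "it is expected that these will include 194 patients with cT1a tumours and 58 patients with cT1b tumours", which is 77% cT1a.
- **Current N.** SAP section 5.1 says "The number of enrolled patients was increased to 300 by a protocol version 8 amendment 7". SAP section 7 keeps the old table and gives no power at 300.

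**The concern.** The stated power can be checked directly, because threshold, alternative, interval, sidedness and level are all given, and it does not reproduce. The table also disagrees with itself. The three specificity rows pose the same test, so they should all need the same number of non-ccRCC patients, yet they imply 73, 67 and 70.

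The figure is used. Specificity determines N, and Scenarios 2 and 3 are offered as possible updates. The IDMC advises at 126 and 189 evaluable cases on whether N is sufficient. Anyone relying on Table 6 for that decision would read 284 or 317 as 90% power, when a single reader has about 80%. At N = 252 a single reader would miss the specificity bound about 17% of the time if true specificity is 0.83, rather than the 10% implied.

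**Working it through.** **Inputs** (Protocol 9.3.1, 9.2.3.1 and Table 6): null 0.68; true specificity 0.83; two-sided 95% Wilson interval, z = 1.960; target power 0.90; 70% cT1a and 30% cT1b; non-ccRCC rates in cT1a/cT1b of 34%/17%, 25%/20% and 25%/15% for Scenarios 1 to 3. Drop-outs are replaced, so N counts evaluable patients.

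**Step 1: expected non-ccRCC patients.** Overall rate r = 0.7 × cT1a rate + 0.3 × cT1b rate.
- Scenario 1: r = 0.238 + 0.051 = 0.289; 252 × 0.289 = 72.8
- Scenario 2: r = 0.175 + 0.060 = 0.235; 284 × 0.235 = 66.7
- Scenario 3: r = 0.175 + 0.045 = 0.220; 317 × 0.220 = 69.7

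**Step 2: exact power at a fixed count n.** Find the smallest number correct, x, whose Wilson lower limit exceeds 0.68. Power is P(X ≥ x) for X ~ Binomial(n, 0.83).

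| n | x needed | Power |
|---|---|---|
| 67 | 54 | 76.0% |
| 70 | 56 | 79.9% |
| 73 | 58 | 83.3% |
| 76 | 60 | 86.2% |
| 86 | 67 | 91.6% |
| 87 | 68 | 90.7% |

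Exact power is saw-toothed in n, but that does not rescue the claim: the best value below n = 86 is 89.7%, at n = 83.

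**Step 3: average over the random count.** The number of non-ccRCC patients is not fixed in advance, so weight the exact power by Binomial(N, r).

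| Scenario | Power at the plan's N | Power at N = 300 | First N reaching 90% |
|---|---|---|---|
| 1 | 83.2% (N = 252) | 89.4% | 307 |
| 2 | 79.5% (N = 284) | 81.8% | 377 |
| 3 | 81.3% (N = 317) | 79.0% | 403 |

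**Step 4: the synopsis split.** 0.34 × 194 + 0.17 × 58 = 75.8 non-ccRCC patients. Power is 86.2% at n = 76 and 84.7% averaged.

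**Step 5: attempt to reproduce the plan's Ns.** The normal-approximation score formula gives the required count as ((1.960 × √(0.68 × 0.32) + 1.2816 × √(0.83 × 0.17)) / 0.15)² = 86.6. A one-sided 5% score calculation gives 69.3, and a two-sided Wald formula gives 65.9. The plan's implied counts (73, 67, 70) lie near the last two, but neither method yields all three Ns and both contradict the stated rule. The cause cannot be established from the documents.

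**Step 6: sensitivity.** The stated Ns of 125, 116 and 114 each imply about 89 ccRCC patients. The rule then needs 71 of 89; power is 83.0% exact and about 80% averaged. This does no harm, because 252 × 0.711 = 179 ccRCC patients give 98.3%.

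**The case against.** **The reader rule.** The plan speaks of the study's power, and the study succeeds if the same two of three readers pass. With fully concordant readers, study-level specificity power equals the per-reader figure. With fully independent readers, 3p² − 2p³ applied to 83.2%, 79.5% and 81.3% gives about 92%, 89% and 91%, close to the stated 90%. This is a fair limit on the claim, and the figures here are therefore per reader. But the readers judge the same scans, so full independence is implausible. The documents give no reader correlation and do not derive the 90% in this way.

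**The recruitment floor.** The synopsis asks for at least 66 ccRCC-negative cT1a patients and allows N to rise to secure them. At a 25% cT1a rate that means 66 / 0.25 = 264 cT1a patients, or about 377 in total at 70/30. Averaged power is then about 90% in Scenario 2 and 88% in Scenario 3. A trial that honoured the floor would not stop at 284 or 317. This softens the practical consequence, but it does not make 90% correct at the Ns printed.

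**The increase to 300.** Under Scenario 1 this nearly restores the target: 89.4% averaged, 90.7% at 87 non-ccRCC patients. SAP section 7 attributes the increase to FDA comments and the key secondary endpoint, and mentions a calculation that it does not show. The old figures still stand in both documents, and nothing is said about power at 300.

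**Conclusion.** The stated 90% is wrong for the rule as written. Per-reader specificity power, averaged over the random non-ccRCC count, is about 83%, 80% and 81% at N = 252, 284 and 317, a shortfall of 7 to 10 percentage points. The synopsis split of 194/58 gives about 85% at 252. At the SAP's N = 300 the figures are about 89%, 82% and 79% for Scenarios 1 to 3.

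These results assume true specificity of 0.83, the plan's non-ccRCC rates and, except where the synopsis split is named, the 70/30 mix. No study-level figure is claimed, because that needs the correlation between readers. The analysis rule, the thresholds and the type I error are sound and are not in question. The correction should be made because this figure sets the trial size and informs the sample-size review.

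**What to change.** Keep the Ns and correct the power, using one measure throughout (averaged over the random non-ccRCC count). This applies to Protocol section 9.3.1, Table 6 and the synopsis, and to SAP section 7 and Table 2.

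- Restate per-reader specificity power as about 83% (252), 80% (284) and 81% (317).
- For 252, say which mix applies: 70/30 (about 83%) or 194/58 (about 85%).
- Add the power at 300: about 89%, 82% and 79% for Scenarios 1 to 3.
- Name the calculation method, and say that the figures are per reader.

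If the sponsor would rather keep 90% in the table, the Ns must change. The averaged measure needs 307, 377 and 403 for specificity and 161, 149 and 146 for sensitivity.

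The cost is a wording and table correction in both documents, with a less favourable stated power. No additional enrolment and no change to endpoints, thresholds or the success rule is required.
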